**Protocol Number: 20170596** 

**Date**: 20 May 2019 Page 1 of 132

**Protocol Number: 20170596** 

**Date**: 20 May 2019 Page 4 of 132

# 1. Protocol Synopsis

**Protocol Title:** An Open-label Phase 2 Study of Carfilzomib Combinations (Carfilzomib Plus Dexamethasone, Carfilzomib Plus Lenalidomide and Dexamethasone, and Carfilzomib Plus Pomalidomide and Dexamethasone), To Assess Tolerability and Adherence in Subjects With Relapsed or Refractory Multiple Myeloma at US Community Oncology Centers

**Short Protocol Title:** A Study of Carfilzomib Combinations in Subjects With Relapsed or Refractory Multiple Myeloma at US Community Oncology Centers

Study Phase: 2

**Indication:** relapsed or refractory multiple myeloma (RRMM)

#### Rationale

The ENDEAVOR study demonstrated the superiority of the combination of carfilzomib (Kyprolis®) with dexamethasone (Kd; 56 mg/m² twice weekly) over bortezomib with dexamethasone (Vd; 1.3 mg/m² twice weekly). Superiority of the Kd regimen was demonstrated in terms of both progression-free survival (PFS) (18.7 months vs 9.4 months, hazard ratio [HR] = 0.53) and overall survival (OS) (median 47.6 months vs 40.0 months, HR = 0.791, one-sided p = 0.010) (Dimopoulos et al, 2016; Dimopoulos et al, 2017). Despite the favorable benefit-risk profile of the Kd regimen, as demonstrated in the ENDEAVOR study, logistical challenges of the twice-weekly dosing have been reported within the United States (US) community practice setting. With the results from the A.R.R.O.W. study, the Kd 70mg/m² once weekly dosing schedule was approved in the US, providing the US practicing centers one more option to treat MM patients with relapse/refractory disease.

Triplet therapy combining a proteasome inhibitor (PI) with an immunomodulatory agent (IMiD) and steroid remains an important and commonly used option for many patients with RRMM. Patients refractory to PIs and IMiDs have extremely poor prognosis with median OS of approximately 13 months and PFS about 5 months (Kumar et al, 2017). Current treatment practices lead to a high prevalence of dual, lenalidomide-bortezomib refractory relapses in later lines of therapy.

The ASPIRE study demonstrated the superiority of the combination of carfilzomib with lenalidomide and dexamethasone (KRd; 27 mg/m² twice-weekly) over lenalidomide with dexamethasone. Superiority of the KRd regimen was demonstrated in terms of median PFS (26.3 vs 17.6 months, HR = 0.69), overall response rate (87.1% vs 66.7%,

Protocol Number: 20170596

**Date**: 20 May 2019 Page 11 of 132

odds ratio = 3.47) (Stewart et al, 2015), health-related quality-of-life (Stewart et al, 2016), as well as OS (median OS: 48.3 vs 40.4 months, HR = 0.79 [Siegel et al, 2018]). Safety results from the final analysis were consistent with the known safety profile of carfilzomib, with no new safety signals observed after extended follow-up.

Despite the favorable benefit-risk profile of the KRd regimen, as demonstrated in the ASPIRE study, compliance with the currently available twice-weekly KRd dosing schedule may be less than optimal because of the convenience-related attributes of this regimen.

Pomalidomide and dexamethasone (Pd) has been approved for subjects with RRMM and has proven efficacy in subjects who were refractory to both bortezomib and lenalidomide. Several phase 2 studies have demonstrated improved efficacy and safety of adding carfilzomib to Pd (KPd) in advanced RRMM compared to historical outcomes with Pd. The key benefits of carfilzomib, pomalidomide, dexamethasone as a triplet-therapy for patients with relapsed and refractory multiple myeloma include increases in PFS, OS, and ORR (San Miguel et al, 2013).

The purpose of this study is to:

- Describe the safety profile of 3 different weekly carfilzomib based regimens:
  - o carfilzomib plus dexamethasone regimen (Kd 56 mg/m² twice weekly in cycles 1-2 followed by Kd 70 mg/m² once weekly in cycles 3–12);
  - carfilzomib plus lenalidomide and dexamethasone regimen (KRd 27 mg/m² twice weekly in cycles 1-2 followed by KRd 56 mg/m² once weekly in cycles 3-12);
  - carfilzomib plus pomalidomide and dexamethasone regimen (KPd 27 mg/m² twice weekly in cycles 1-2 followed by KPd 56 mg/m² once weekly in cycles 3-12) in subjects with RRMM with 1–3 prior lines of therapy at study entry.
- Describe subjects' adherence these carfilzomib based regimens.

Protocol Number: 20170596

**Date:** 20 May 2019 Page 12 of 132

# **Objectives/Endpoints**

Objectives	Endpoints
Primary	
Describe adherence and treatment safety across all 12 cycles of carfilzomib based regimens in subjects with relapsed or refractory multiple myeloma with 1-3 prior lines of therapy at study entry.	
 
proportion of subjects completing         12 cycles of treatment
 
proportion of actual cumulative dose         received to the full intended cumulative         dose in cycles 1-12
 
relative dose intensity in cycles 1-12
 
dose modifications and reasons in         cycles 1-12
 
treatment-emergent adverse events and         serious adverse events
 

Secondary	
Assess subject health-related quality-oflife (HRQoL) with the Kd, KRd, and KPd regimens.	European Organization for Research and Treatment of Cancer Quality-of-life Questionnaire (EORTC QLQ) Core 30 (C30) and EORTC QLQ Multiple Myeloma Module (MY20) scores through cycle 12 or up to disease progression
Assess response to the Kd, KRd, and KPd regimens.	
 
response rate (stringent complete response [sCR], complete response [CR], very good partial response [VGPR], partial response [PR], minimal response [MR], stable disease [SD], progressive disease [PD], Not evaluable [NE]).
 
progression-free survival (PFS) at 1 year
 
response rate and PFS by line of prior therapy 1 vs ≥ 2
 

# **Hypotheses**

Carfilzomib combinations (Kd, KRd, and KPd) have acceptable tolerability and adherence in subjects with RRMM in a community-based setting.

#### **Overall Design**

This is a phase 2, multicenter, open-label study in subjects with RRMM in US community oncology centers. Subjects with 1-3 prior lines of therapy at study entry are eligible to be screened for participation. Subjects refractory to their last line of treatment are eligible to participate as long as their last line of treatment did not include a proteasome inhibitor (PI). The study will consist of a screening period of up to 28 days for bone marrow aspirate, bone lesion assessment, and plasmacytoma assessment and up to 21 days for all other assessments, up to 12 cycles of treatment, and a 30-day safety follow-up period following the last dose of study drug.

Protocol Number: 20170596

**Date**: 20 May 2019 Page 13 of 132

During the treatment period, subjects in the Kd arm will be treated with Kd 20/56 mg/m² twice weekly for two 28-day cycles followed Kd 70 mg/m² once weekly for an additional ten 28-day cycles; subjects in the KRd arm will be treated with KRd 20/27 mg/m² twice weekly for two 28-day cycles followed by KRd 56 mg/m² once weekly for an additional ten 28-day cycles; and subjects in the KPd arm will be treated with KPd 20/27 mg/m² twice weekly for two 28-day cycles followed by KPd 56 mg/m² once weekly for an additional ten 28-day cycles.

After discontinuation of study drugs, subjects in all treatment arms will be followed for 30 days for safety.

### **Number of Subjects**

A total of approximately 75 subjects will be enrolled in the study, with approximately 25 subjects in each arm.

#### **Summary of Subject Eligibility Criteria**

This study will enroll adults ≥ 18 years of age with RRMM. Subjects must have measurable disease, Eastern Cooperative Oncology Group Performance Status (ECOG PS) of 0 to 1, and at least PR to at least 1 line of prior therapy. Subjects must also have received at least 1 but not more than 3 prior lines of therapy for multiple myeloma (MM).

For a full list of eligibility criteria, please refer to Section 6.1 to Section 6.2.

#### **Treatments**

#### For all arms

Dexamethasone will be taken orally or by IV infusion at a dose of 20 mg once-daily on days 1, 2, 8, 9, 15, 16, 22, and 23 of cycles 1-2, and at a dose 40 mg once-daily on days 1, 8, 15 of cycles 3-12. All doses should be administered on the scheduled days  $\pm$  2 days but prior to carfilzomib infusion except for days 22 and 23 of cycles 1-2.

Dexamethasone will be administered at least 30 minutes (but no more than 4 hours) prior to carfilzomib. Subjects receiving dexamethasone IV on days 1, 2, 8, 9, 15, and 16, may receive the day 22 and day 23 dose orally.

#### Kd arm

Carfilzomib will be administered in the clinic by a qualified healthcare provider as an intravenous (IV) infusion.

Carfilzomib will be administered at 20 mg/m^2 on days 1 and 2 of the first cycle (see Table 7-1). After that, carfilzomib will be administered at 56 mg/m^2 on days 8, 9,

Protocol Number: 20170596

**Date:** 20 May 2019 **Page 14 of 132** 

15, and 16 of the first cycle, and then on days 1, 2, 8, 9, 15, and 16 for cycle 2. Starting with cycle 3 through cycle 12, carfilzomib will be administered at 70 mg/m $^2$  on days 1, 8, and 15 of each 28-day cycle. All doses should be administered on the scheduled day  $\pm$  2 days, and the day 8 and 15 doses should have at least a 5-day treatment-free interval.

## KRd arm

Carfilzomib will be administered in the clinic by a qualified healthcare provider as an IV infusion.

Carfilzomib will be administered at 20 mg/m² on days 1 and 2 of the first cycle (see Table 7-1). After that, carfilzomib will be administered at 27 mg/m² on days 8, 9, 15, and 16 of the first cycle, and then on days 1, 2, 8, 9, 15, and 16 for cycle 2. Starting with cycle 3 through cycle 12, carfilzomib will be administered at 56 mg/m² on days 1, 8, and 15 of each 28-day cycle. All doses should be administered on the scheduled day  $\pm$  2 days, and the day 8 and 15 doses should have at least a 5-day treatment-free interval.

Lenalidomide will be taken QD orally at a dose of 25 mg on days 1 to 21 of each cycle (cycles 1-12).

#### KPd arm

Carfilzomib will be administered in the clinic by a qualified healthcare provider as an IV infusion.

Carfilzomib will be administered at 20 mg/m² on days 1 and 2 of the first cycle (see Table 7-1). After that, carfilzomib will be administered at 27 mg/m² on days 8, 9, 15, and 16 of the first cycle, and then on days 1, 2, 8, 9, 15, and 16 for cycle 2. Starting with cycle 3 through cycle 12, carfilzomib will be administered at 56 mg/m² on days 1, 8, and 15 of each 28-day cycle. All doses should be administered on the scheduled day  $\pm$  2 days, and the day 8 and 15 doses should have at least a 5-day treatment-free interval.

Pomalidomide will be taken QD orally at a dose of 4 mg on days 1 to 21 of each cycle (cycles 1-12).

#### **Procedures**

Written informed consent must be obtained from all subjects before any study-specific screening procedures are performed.

Protocol Number: 20170596

**Date**: 20 May 2019 Page 15 of 132

# Screening procedures will include:

 Collection of medical history; physical examination and measurements, electrocardiogram (ECG), vital signs, ECOG PS, echocardiogram, and pregnancy test for females of childbearing potential (FCBP).

Multiple myeloma disease assessments to confirm measurable disease: serum
protein electrophoresis (SPEP), urine protein electrophoresis (UPEP), serum free
light chain (SFLC), serum immunofixation (SIFE), urine immunofixation (UIFE),
plasmacytoma evaluation, bone lesion assessment, and bone marrow aspirate with
fluorescence in-situ hybridization (FISH).

At specified visits, outlined in the Schedule of Activities (Table 2-1), the following measurements will be collected: weight, vital signs, recording of concomitant medications, as well as review of adverse events and serious adverse events. Blood will be collected for local laboratory testing, including hematology and chemistry. Additionally, in FCBP a urine or serum pregnancy test will be performed locally.

Investigators are required to follow International Myeloma Working Group (IMWG) criteria for assessment of response and disease progression (see Section 12.8). Disease assessments based on local laboratory data will be performed per the Schedule of Activities (Table 2-1) and include: SPEP, UPEP, SFLC, SIFE, UIFE.

Clinical outcome assessments (COAs) will be measured using 3 questionnaires:

HRQoL and

For a full list of study procedures, including the timing of each procedure, please refer to Section 9.2 and the Schedule of Activities in Table 2-1.

#### Statistical Considerations

With a sample size of 25 subjects in each treatment arm, assuming 50%, 75%, or 90% of subjects complete 12 cycles of treatment, the expected half-widths of the 95% confidence interval (CI) for estimating the proportion of subjects completing 12 cycles of treatment are provided below.

	95% Cd	onfidence Interval Half-w	idth (%)
Sample Size	50%	75%	90%
25	20.5	18.1	13.5

The full analysis set will be the same as the safety analysis set, which will include all enrolled subjects who received at least 1 dose of any study treatment (ie, carfilzomib, lenalidomide, pomalidomide, or dexamethasone). Unless otherwise specified, following analyses will be based on the safety analysis set.

Protocol Number: 20170596

**Date**: 20 May 2019 Page 16 of 132

For primary endpoints, the proportion of subjects completing 12 cycles of carfilzomib based regimens will be calculated. The proportion of actual cumulative dose received to the full intended cumulative dose in cycles 1-12 will be summarized descriptively. The full intended cumulative dose is defined as all therapy specified per

Sections 7.1.1.2 and 7.1.2 without consideration for dose modification or skipped doses.

Relative dose intensity in cycles 1-12 will be summarized descriptively. Dose modifications including dose reduction, dose withheld, and dose delay in cycles 1-12 will be summarized along with reasons including adverse events and non-adverse events.

Treatment-emergent adverse events and serious adverse events in cycles 1-12 will be summarized descriptively following the methods specified in Section 10.3.2.3. The proportions of treatment discontinuations due to all adverse events, reasons for treatment discontinuation due to all adverse events, and dose reductions due to all adverse events will be summarized descriptively.

All EORTC QLQ-C30 and EORTC QLQ-MY20 subscale scores up to cycle 12 or disease progression will be summarized descriptively by cycle based on the safety analysis set. The rate of PFS at 1 year will be estimated using the Kaplan-Meier method and with CI estimated using the method by Kalbfleisch and Prentice, 1980 with log-log transformation. The response rate and 1-year PFS rate will be summarized descriptively by line of prior therapy 1 vs  $\geq$  2.

For a full description of statistical analysis methods, please refer to Section 10.

Sponsor Name: Amgen Inc.

[figure not shown]
Protocol Number: 20170596

**Date:** 20 May 2019 Page 17 of 132

# 2. Study Schema and Schedule of Activities

# 2.1 Study Schema

Figure 2-1. Study Schema

EOT = end of treatment; d = dexamethasone; K = Kyprolis (carfilzomib); P = pomalidomide; QD = once daily; R = lenalidomide

<sup>a All screening assessments except bone marrow aspirate, bone lesion assessment, and plasmacytoma assessment must be completed within 21 days before cycle 1 day 1. Bone marrow aspirate, bone lesion assessment, and plasmacytoma assessment must be completed within 28 days of cycle 1 day 1.

**Protocol Number: 20170596** 

**Date:** 20 May 2019 **Page 18 of 132** 

# 2.2 Schedule of Activities

Table 2-1. Schedule of Activities

		Screening a b (up to			•	Trea	atm	ent	Peri	iod					Safety FU c (30 [+3]	
		21 days			Су	cle	1-2				C	ycle	e 3-	-12		
PROCEDURE		before Day 1)	Day 1	2	8	9	15	16	22	23	1	8	15	21	days post last dose)	
GENERAL ANI	SAFETY ASSE	SSMENTS	-		•	•	•	•				•				
Informed conse	nt	Х														
Inclusion and ex	xclusion criteria	Х														
Demographics		Х														
Physical examin	nation	X													X	
	Height, BMI	X														BSA should be calculated per Mosteller
Physical measurements	Weight	Х	Х								Χ					formula and utilized to calculate required study drug doses. BSA should
	BSA	Х	(X)													be recalculated if weight changes by 20% or more (gain or loss)
Medical history		X														
Cardiac history		X														See Section 9.2.1.3
Substance use		X														
ECG		X														
Vital signs		Х	Х	Х	Х	Х	Х	Х			Χ	Χ	Х		X	Checked prior to administration of study drug(s) in all cycles.
ECOG performa	ance status	Х													Х	
Echocardiogran	n	Х														At screening and as clinically indicated (per Section 12.9)
Adverse events events	/serious adverse					С	onti	nuo	us							Adverse events are to be captured during screening, starting with the signing of the informed consent. Recommended dyspnea evaluation per investigator's judgment per Section 12.9

**Protocol Number: 20170596** 

**Date:** 20 May 2019 **Page 19 of 132** 

Table 2-1. Schedule of Activities

			1	ıa	bie	Z- I	. 3	CII	euu	ne e	UI F	1 Cu	viu	es	1		
			Screening a b (up to						nt F	Peri	od				Safety FU°		
			21 days before		1	Cyc	le 1	 -2				Су	cle	3-12	(30 [+3] days post		
PROCEDU	RE		Day 1)	Day 1	2	8	9	15	16	22	23	1	8	15 21		Notes	
Concomita	nt thera	pies review					Сс	ntir	านอน	IS							
LABORAT		SSESSMENTS															
	Kd Arm	Urine or serum	X	Х								Х			Х		
		Serum	X												Χ		
		Urine or serum cycle 1 (predose)		Х		х		X		Х							
Pregnancy test (FCBP only) d	and KRd	Urine or serum cycle 2 to 12 (predose; regular menses)		х								х				Within 24 hours prior to dose of lenalidomide or pomalidomide for subjects in the KRd or KRd or a respectively.	
	Arms	Urine or serum cycle 2 to 12 (predose; irregular menses)		Х				X				X		Х		in the KRd or KPd arms, respectively	
Hematology	у	, ,	х	Х								Х			Х	Hematology and chemistry samples from screening may be used for C1D1 if taken within 3 days prior to C1D1. Lab	
Chemistry			Х	×								X			X	results must be evaluated for potential dose modification assessment prior to dosing (see Section 7.4). Chemistry and hematology assessments, other than for C1D1, may be taken within 2 days prior to the scheduled assessment.	

Page 2 of 7

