#### 3.3.3.1.11 Hepatic Toxicity

The subject incidence of hepatic toxicity was 1.9% with a subject incidence of 0.7% for serious events. Cases of hepatic failure, including fatal cases, have been reported in < 1% of subjects in clinical studies with carfilzomib. Serial monitoring of liver enzymes is conducted every 28 days throughout treatment period (see Schedule of Activities,

Protocol Number: 20170596

**Date**: 20 May 2019 Page 37 of 132

Table 2-1). Dose modification guidance for hepatic toxicity (including stopping carfilzomib) is provided in Section 7.4.

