## 7.1.1.2.1 Starting Dose in Hepatic Insufficiency

For subjects with mild hepatic insufficiency during screening, the initial dose of carfilzomib on days 1 and 2 of cycle 1 should be reduced by 25% to 15 mg/m². For subjects in the Kd arm, starting on day 8 and for all subsequent doses of carfilzomib during cycles 1 and 2, the dose should be 42 mg/m² (Brown et al, 2017); the dose in cycle 3 through 12 should be 53 mg/m². For subjects in the KRd and KPd arms, starting on day 8 and for all subsequent doses of carfilzomib during cycles 1 and 2, the dose should be 20 mg/m² as per the protocol and doses in cycles 3 through 12 should be 42 mg/m².

If hepatic function returns to normal, the dose in following cycles may be re-escalated to the full dose per the protocol. For dose modification due to subsequent changes in hepatic function, refer to Section 7.4.1.1.3 (Table 7-4).

Protocol Number: 20170596

**Date:** 20 May 2019 Page 52 of 132

Mild and moderate hepatic dysfunction is defined as:

Mild: bilirubin > 1.0-1.5 x ULN, or AST > ULN with bilirubin ≤ ULN

Moderate: bilirubin > 1.5-3.0 x ULN with any AST

Grade 3 elevation in ALT and/or AST (> 5x ULN)

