#### 7.4 Dose Modification

# 7.4.1 Dosage Adjustments, Delays, Rules for Withholding or Restarting, Permanent Discontinuation

# 7.4.1.1 Amgen Investigational Product: Carfilzomib

The reason for dose change of carfilzomib is to be recorded on each subject's CRF.

Carfilzomib may be discontinued, temporarily delayed, or dosage temporarily reduced, in the event of a treatment-related toxicity that, in the opinion of the investigator, warrants the discontinuation, temporary delay or dose reduction. Carfilzomib dose must be modified based on specified toxicities, as indicated in Table 7-3 and Table 7-4. The subject will be considered on protocol treatment while receiving carfilzomib. Carfilzomib (both twice-weekly and once-weekly regimen) must be discontinued permanently if a delay of more than 6 weeks is required due to unresolved toxicity.

If day 1 of a cycle is delayed, day 1 of subsequent cycles should be adjusted accordingly to maintain the 28-day cycle duration. However, if a within-cycle dose is delayed, then the dates of the subsequent within-cycle doses should not be adjusted.

Protocol Number: 20170596

**Date**: 20 May 2019 Page 58 of 132

If carfilzomib administration does not commence within the allowable window of the scheduled administration date, then the dose will be considered a missed dose. Administration may resume at the next planned dosing date. A missed dose will not be made up.

If either carfilzomib or dexamethasone are held for the remainder of the previous cycle or the new cycle is delayed due to residual toxicity on the planned day 1 of the next cycle, then the new cycle will be started at 1 dose decrement for the drug(s) causing the delay.

For conditions that do not require carfilzomib dose reduction, refer to Section 7.4.1.3.

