**Protocol Number: 20170596** 

**Date**: 20 May 2019 Page **60 of 132** 

Table 7-4. Dose Modification Guidelines for Nonhematologic Toxicities

For grading criteria, see CTCAE grading scale in Section 12.4.			
Symptom/Sign/Investigation	Recommended Action		
Renal Dysfunctiona:			
Estimated GFR ≥ 15 mL/min/1.73 m 	Full dose. For acute deterioration requiring dialysis, see below.		
Estimated GFR < 15 mL/min/1.73 m  (NCI-CTCAE grade 4)	Hold dose until estimated GFR returns to ≥ 15 mL/min/1.73 m², then resume same dose. If dialysis is required (regardless of estimated GFR levels), use the maximal dose of 20 mg/m² and administer carfilzomib after dialysis.		
Chronic dialysis stable for ≥ 30 days	Dose may be re-escalated up to full dose as clinically tolerated (see Section 7.4.1.1.4. for dose re-escalation). Carfilzomib must be administered after dialysis.		
Hepatic Dysfunction and Related Investi	gations		
Mild to moderate liver dysfunction:	25% dose reduction.		
defined as 2 consecutive values, at least 28 days apart, of: (1) total bilirubin (> 33% direct) > 1x ULN to < 3x ULN OR	Dose may be re-escalated if liver function tests return to normal and drug-induced hepatotoxicity is excluded.		
(2) an elevation of AST and/or ALT with normal bilirubin			
Grade 3 elevation in bilirubin (> 3x ULN), ALT and/or AST (> 5x ULN)	Hold carfilzomib until resolution to baseline or normal.  Monitor any abnormality weekly. Resume carfilzomib with a 25% dose reduction for 1 full cycle if drug-induced hepatotoxicity is excluded. If no worsening in the total bilirubin, AST or ALT on the reduced dose for 1 full cycle, dose may be re-escalated, if drug induced hepatotoxicity is excluded (see Section 7.4.1.1.4 for dose re-escalation instructions).		
Drug-induced hepatotoxicity (attributable to carfilzomib)	Discontinue carfilzomib.		
Other Nonhematologic Toxicities			
Tumor lysis syndrome: 3 or more of the following:  • increase in creatinine of ≥ 50%  • increase in uric acid of ≥ 50%  • increase in phosphate of ≥ 50%  • increase in potassium of ≥ 30%  • decrease in calcium OR  • increase in LDH of ≥ 2-fold from baseline	Hold carfilzomib until all abnormalities in serum chemistries have resolved; resume at full dose.		
	Page 1 of '		

Page 1 of 3

Footnotes defined on last page of this table.

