#### 12.2 Appendix 2. Clinical Laboratory Tests

The tests detailed in Table 12-1 will be performed by a local laboratory.

Protocol-specific requirements for inclusion or exclusion of subjects are detailed in Sections 6.1 to Section 6.2.

Additional tests may be performed at any time during the study as determined necessary by the investigator or required by local regulations.

Table 12-1. Analyte Listing

		Analyte Listing	
Screening only	Chemistry	Hematology	Other Labs
β-2 microglobulin	Albumin	Hemoglobin	Serum or Urine
Bone marrow	ALP	Hematocrit	Pregnancy
aspirate with FISH	ALT (SGPT)	Platelets	
Creatinine	AST (SGOT)	RBC	
Glucose (fasting)	Bicarbonate	WBC	
HbA1c	BUN or Urea	Differential	
LDH	Calcium	
 
Bands/stabs
 
	
Lipid panel (fasting):	Chloride	
 
Eosinophils
 
	
•Total cholesterol	Creatinine	
 
Basophils
 
	
•HDL	Glucose	
 
Lymphocytes
 
	
•LDL	Magnesium	
 
Monocytes
 
	
•triglycerides	Phosphorus	
 
Neutrophils
 
	
NT-proBNP (or BNP) a	Potassium		
SFLC	Sodium		
SIFE	Total bilirubin		
SPEP	Direct bilirubin		
UIFE	Total protein		
UPEP			
Uric acid			
Urine albumin			
Urine creatinine		( AOT ( )	

ALP = alkaline phosphatase; ALT = alanine aminotransferase; AST = aspartate aminotransferase;

BNP = brain natriuretic peptide; BUN = blood urea nitrogen; FISH = fluorescence in-situ hybridization;

HbA1c = hemoglobin A1c; HDL = high-density lipoproteins; LDH = lactate dehydrogenase;

LDL = low-density lipoproteins; NT-proBNP = N-terminal of the prohormone brain natriuretic peptide;

RBC = red blood cells; SFLC = serum free light chain; SGOT = serum glutamic oxaloacetic transaminase;

SGPT = serum glutamate-pyruvate transaminase; SIFE = serum immunofixation electrophoresis;

SPEP = serum protein electrophoresis; UIFE = urine immunofixation electrophoresis;

UPEP = urine protein electrophoresis; WBC = white blood cells.

a Either NT-proBNP or BNP may be used per investigator's discretion.

Protocol Number: 20170596

**Date**: 20 May 2019 Page 95 of 132

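### Table 7-4's 28-day minimum for the 25% carfilzomib reduction has no tolerance for the 2-day early draw allowed in Table 2-1, so a compliant pair of abnormal liver tests can miss the trigger (minor)

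*Protocol*

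**What the plan says.** **Schedule.** Protocol Table 2-1 places chemistry on day 1 of each 28-day cycle, and Section 3.3.3.1.11 says the same of liver tests: "Serial monitoring of liver enzymes is conducted every 28 days throughout treatment period". The Table 2-1 note makes these samples the input for dosing, because results have to be reviewed against Section 7.4 before the dose is given. A screening sample up to 3 days old may serve for C1D1. After that: "Chemistry and hematology assessments, other than for C1D1, may be taken within 2 days prior to the scheduled assessment". The window opens early only; there is no late side.

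**Trigger.** In Table 7-4, the mild to moderate liver dysfunction row calls for a 25% dose reduction. The condition is "2 consecutive values, at least 28 days apart" of raised bilirubin, or of raised AST and/or ALT with normal bilirubin. No tolerance is stated and there is no reference to the draw window.

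**Force.** Section 7.4.1.1 states: "Carfilzomib dose must be modified based on specified toxicities, as indicated in Table 7-3 and Table 7-4". The same paragraph also lets the investigator act on a treatment-related toxicity that, "in the opinion of the investigator, warrants the discontinuation, temporary delay or dose reduction".

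**Extra tests.** Appendix 2 (Section 12.2) adds: "Additional tests may be performed at any time during the study as determined necessary by the investigator or required by local regulations".

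**The concern.** The rule asks for a gap of at least 28 days between two values that the schedule places exactly 28 days apart. The only deviation allowed for a later draw is to take it early, so use of that window can only shorten the gap from the previous draw. A site that follows both tables can then hold two consecutive abnormal results and have no reduction triggered.

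What is at stake is consistency of dosing. Two subjects with the same persistent lower-grade abnormality could receive different carfilzomib doses because of the day on which blood was drawn. Dose modifications and relative dose intensity are among the primary endpoints (Section 4.1), so it is better that draw-day habits do not feed into them.

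**Working it through.** **Inputs.** Cycle length 28 days (Section 7.4.1.1). Draws after C1D1 are 0, 1 or 2 days early, and the C1D1 sample 0 to 3 days early (Table 2-1, counted in whole days). Minimum gap 28 days and a 25% cut (Table 7-4). Doses from Table 7-1.

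**Gap between scheduled draws, day 1 on time.** If the first draw is *a* days early and the second *b* days early, gap = 28 + *a* − *b*. With *a* = *b* = 0 this gives the protocol's nominal 28 days.

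| Gap (days) | 26 | 27 | 28 | 29 | 30 |
|---|---|---|---|---|---|
| Combinations of 9 | 1 | 2 | 3 | 2 | 1 |

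- The gap is short exactly when *b* > *a*: (0,1) = 27, (0,2) = 26, (1,2) = 27. That is 3 of 9, and it applies to the 10 pairs from C2D1–C3D1 to C11D1–C12D1.
- For C1D1–C2D1, *a* runs from 0 to 3. The gaps run from 26 to 31 days and 3 of 12 are short.
- If *b* = 0 or *b* = *a*, the gap is never under 28.

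**How long the miss can last.** Two short pairs in a row need the offsets 0, 1, 2 (1 of 27 combinations). Three in a row would need four increasing offsets from three values, which is impossible. The usual delay is therefore one cycle.

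**Share of pairs.** The documents give no distribution of draw days, so this is an assumed range. For independent draws with probabilities p0, p1, p2 of being 0, 1, 2 days early, P(*a* < *b*) = p0(p1 + p2) + p1·p2:

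- Constant offset at a site: 0.
- 90/5/5%: 0.90 × 0.10 + 0.05 × 0.05 = 0.0925, or 9%.
- 80/10/10%: 0.80 × 0.20 + 0.10 × 0.10 = 0.17, or 17%.
- Uniform: 1/3 × 2/3 + 1/9 = 0.333, or 33%.

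These are shares of pairs of draws. They matter only in subjects whose liver tests stay abnormal.

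**Dose consequence.** Intended carfilzomib over 12 cycles:

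- Kd: 2×20 + 4×56 + 6×56 + 30×70 = 2,700 mg/m².
- KRd and KPd: 2×20 + 4×27 + 6×27 + 30×56 = 1,990 mg/m².

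In cycles 3-12, each dose given unreduced exceeds the reduced dose by 0.25 × 70 = 17.5 (Kd) or 0.25 × 56 = 14 mg/m² (KRd, KPd).

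| Unreduced doses before the cut | Kd | KRd, KPd |
|---|---|---|
| 3 (no repeat test) | 52.5 (1.9%) | 42 (2.1%) |
| 2 (repeat accepted, day 15) | 35 (1.3%) | 28 (1.4%) |
| 1 (repeat accepted, day 8) | 17.5 (0.65%) | 14 (0.70%) |
| 0 (repeat read before dosing on day 1) | 0 | 0 |

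The repeat rows assume that the repeat may be paired with the first scheduled value. Repeats on days 1, 8 and 15 fall 28–30, 35–37 and 42–44 days after it. If consecutive means adjacent draws, a day 8 repeat follows the early second draw by only 8 or 9 days and does not complete the pair. Table 7-4 does not say which reading applies.

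These figures exclude a miss at C1D1–C2D1, which would affect six doses in cycle 2, and the earlier Kd subjects who stay on twice-weekly dosing through cycle 6 (Section 7.1.1.2).

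**The case against.** The best reply is that nothing forces a miss. The window is optional. The site knows of the first abnormal value a cycle ahead and can draw the second sample at the day 1 dosing visit, or at the same offset as before, and meet the rule without an extra sample. A strict 28-day persistence requirement is a reasonable choice for lower-grade abnormalities. Table 7-4 presents its entries as recommended actions, and the investigator may retest or reduce at discretion. All of this stands, and it is why the point is minor. It does not remove the mismatch, because each remedy depends on the site noticing the problem. The discretion clause is also tied to treatment-related toxicity, whereas this row of Table 7-4 requires no attribution.

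A reader might infer that the rule is disabled or that serious liver toxicity goes unmanaged. The documents do not support that. Most offset combinations meet the rule, and a miss usually corrects itself at the next draw. Grade 3 elevations have their own row: "Hold carfilzomib until resolution to baseline or normal". Hepatotoxicity attributed to carfilzomib leads to discontinuation. Section 7.1.1.2.1 covers baseline abnormality: "For subjects with mild hepatic insufficiency during screening, the initial dose of carfilzomib on days 1 and 2 of cycle 1 should be reduced". None of these needs the 28-day pair.

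A reader might also take the 33% as a share of subjects. It is a share of draw pairs under one assumed pattern, and 0% is equally compatible with the documents.

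**Conclusion.** The plan is wrong as written on this point, and the error is minor. With day 1 on time, 3 of 9 compliant offset combinations (3 of 12 for C1D1–C2D1) are 26 or 27 days apart and miss a reduction that Section 7.4.1.1 makes mandatory. If the second draw is not on day 1 or at the same offset, no qualifying repeat is taken and the investigator does not act on discretion, the cut usually comes one cycle late. In cycles 3-12 that is about 2% of the intended 12-cycle carfilzomib dose for that subject.

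The documents do not give the number of subjects affected. The pooled hepatic toxicity incidence of 1.9% in Section 3.3.3.1.11 would be about 1.4 of 75 subjects (0.019 × 75). It is a poor proxy, since mild laboratory abnormalities may be more common. Section 10.1 describes the study as descriptive, so no test or decision changes.

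The gap range assumes that day 1 is on time. A delayed day 1 lengthens the gap. If the scheduled draw moves with the ±2-day dosing window of Section 7.1.1.2, which the protocol does not settle, compliant gaps could be as short as 22 days: a first visit 2 days late with no early draw, then a visit 2 days early with a draw 2 days before it, gives 28 − 4 − 2.

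**What to change.** Reword the Table 7-4 condition for mild to moderate liver dysfunction along these lines: *abnormal at 2 consecutive scheduled cycle day 1 assessments (each drawn within its permitted window), with any unscheduled value in between also abnormal*.

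State no minimum number of days. A 26-day floor would work only with day 1 on time and would fail again if the draw follows a shifted dosing day. Without a day count, all 9 offset combinations qualify (12 of 12 for C1D1–C2D1). Persistence across a cycle is still required, and an abnormal recheck no longer resets the rule. The Grade 3 and drug-induced hepatotoxicity rows stay as they are.

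The downside is that a few reductions will occur one cycle earlier. The cost is one reworded condition, which can go into the next amendment with the IRB submission described in Section 12.3. No extra samples, visits or subjects are needed.
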